1.2. Secondary Objectives

- Evaluate the toxicities of HD IL-2 in this patient population (CTCAE v.4).
- Evaluate the progression free survival (PFS) and overall survival (OS).
- Test laboratory correlative studies within the circulation and the tumor microenvironment (TME) to better understand the impact of HD IL2 in this setting.

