2.2. High Dose Interleukin-2

IL-2 plays a central role in immune regulation as it affects the survival of key cells of the immune system that are responsible for the antitumor cytotoxicity of T-lymphocytes and natural-killer (NK) cells, and it has a cofactor role in the activation of B cells and macrophages [5]. The administration of IL-2 at high bolus IV doses once every eight hours was a regimen developed by the National Cancer Institute (NCI) based on animal models indicating that antitumor activity with this agent was dose-dependent [6-8]. Initial studies with HDB IL-2 utilized doses of 600,000-720,000 units/kg every 8 hours from days 1-5 (cycle 1) and days 15-19 (cycle 2) with a maximum of 14 doses per cycle or 28 doses per course (1 course = 2 cycles). Responding or stable patients were offered a second course of therapy 8-12 weeks later. IL-2 was administered either as a single agent or in combination with immunologically active cells, so-called adoptive immunotherapy. The latter technique utilized two types of immune cells: the lymphokine-activated-killer (LAK) cells and the tumor infiltrating lymphocytes (TIL). Eight clinical trials conducted between 1985 and 1993 and using the HDB IL-2 regimen described above, with or without LAK cells, were reviewed in a retrospective analysis. These trials had an enrollment of 270 patients with advanced metastatic melanoma [7-11]. In those studies that involved the concurrent administration of LAK cells, these cells were obtained using leukapheresis from patients during the rebound lymphocytosis that occurs following treatment and cessation of bolus IL-2 (days 8 to 12). LAK cells were then cultured in IL-2 for 3 to 4 days. These generated LAK cells were reinfused with IL-2 during the second cycle of IL-2 administration. The retrospective analysis of these trials with a follow-up through December 1998 along with a more recent update demonstrated an objective response rate of 16% with durable responses in 4% of patients [2, 10-12]. The median response duration was 8.9 months (range 4 to 106+ months). Twenty eight percent of the responding patients, including 59% of those patients who had achieved a complete response, have remained progression free at a median follow-up of 62 months. Furthermore, no patient who had responses longer than 30 months has relapsed, suggesting the possibility that these patients may be “cured”. The frequency of the responses was similar in patients with visceral metastases and/or large tumor burdens, but the responses were less in patients with poor performance status or those who had received prior systemic therapy. Based on these data, HDB IL-2 received approval by the US-FDA for the treatment of metastatic melanoma [11-13]. In addition to being logistically challenging, randomized studies have not shown superiority for IL-2 administered with LAK cells versus therapy with HD IL-2 alone [12-14]. Furthermore, a randomized phase III trial of CD8+ TIL given in combination with rIL-2 in metastatic renal cell carcinoma has been negative [13-15]. We have previously shown that HD IL2 is an active therapy for patients who progress on biochemotherapy; this observation has implications regarding the importance of dose intensity for IL-2 therapy [16]. Continuous infusion of IL-2 at intermediate dosage is a critical component of biochemotherapy regimens and it was previously unknown whether patients treated with biochemotherapy and failing to obtain response, or responding and then demonstrating progression, are capable of subsequently responding and benefiting clinically from the HD IL2 regimen.

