5.2. Aldesleukin (Interleukin-2) Administration

Aldesleukin (Interleukin-2, IL-2) will be administered on an inpatient basis. Reported adverse events and potential risks for aldesleukin are described in Section 7.

- Patients will receive a total of 6 cycles (1 cycle = 5 days) of IL-2 as described in section 5.1. A cycle of IL-2 may be delayed for up to 2 weeks in case of unresolved toxicity.
- Aldesleukin will be administered at 600,000 IU/kg IV bolus q 8 hours during

days 1-5 of each cycle (maximum 14 doses per 5 day cycle).

- As all institutions participating in this protocol have established and experienced high dose interleukin-2 programs, the administration of aldesleukin (at the protocol's specified dose and frequency) and the dose delay/discontinuation criteria during a cycle of IL-2 will follow the institutional standard of care guidelines. Useful guides are provided by:
 - Schwartzentruber DJ. J Immunother. 2001 Jul-Aug;24(4):287-93[20].
 - Janice P Dutcher, Douglas J Schwartzentruber, Howard L Kaufman, Sanjiv S Agarwala, Ahmad A Tarhini, James N Lowder and Michael B Atkins. High Dose Interleukin-2 (Aldesleukin) - Expert Consensus on Best Management Practices—2014. Journal for Immunotherapy of Cancer 2014, 2:26 (16 September 2014).

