Toxicity will be primarily evaluated by examining the number of doses of HD IL-2 administered during a cycle of therapy. Based on previous experience with high dose IL2 at the University of Pittsburgh, the median number of doses per course 1 (first 2 cycles) as monotherapy [16], is 16 (range 8-26) and in sequential combination with temozolomide [21], is 15 (range 7-23). As a result, the median number of doses per course 1 will be considered in addition to toxicity reported via CTCAE criteria.

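### Section 11.3.5 makes doses per cycle the primary toxicity measure, but its reference medians are per course 1, the objective is CTCAE toxicity, and a dose count alone cannot separate toxicity from attrition

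*Combined protocol and SAP*

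**What the plan says.** Section 11.3.5 (Safety) opens with the rule "Toxicity will be primarily evaluated by examining the number of doses of HD IL-2 administered during a cycle of therapy". It then gives two reference values from one university's experience. For monotherapy, "the median number of doses per course 1 (first 2 cycles) as monotherapy [16], is 16 (range 8-26"; for the other regimen, "in sequential combination with temozolomide [21], is 15 (range 7-23". It closes by saying that "the median number of doses per course 1 will be considered in addition to toxicity reported via CTCAE criteria". It gives no threshold, test or interval for either the dose count or the CTCAE data.

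The secondary objective in section 1.2 is "Evaluate the toxicities of HD IL-2 in this patient population (CTCAE v.4"; it does not mention dose count. Section 6.4 likewise bases ongoing safety review on the NCI toxicity criteria. The safety population in section 11.3.1 is everyone who received initial treatment.

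On how doses come to be omitted, section 5.2 says that "the dose delay/discontinuation criteria during a cycle of IL-2 will follow the institutional standard of care guidelines". Section 5.4 ends treatment for progression, intercurrent illness, withdrawal and non-compliance as well as for adverse events.

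**The concern.** Three things in this short section do not fit together.

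- **Unit.** The opening sentence counts doses in one cycle. The reference medians and the closing sentence count doses in course 1, which is two cycles. An analyst cannot tell which variable is the primary one, which of up to six cycles the opening sentence means, or how cycles would be combined.
- **Objective.** The objective is toxicity graded by CTCAE, yet the analysis text ranks a dose count first and specifies no CTCAE summary. Response rate and median PFS and OS, by contrast, are each given 90% limits.
- **Specificity.** A course-1 dose count measures treatment delivered. A patient who stops after cycle 1 for progression lowers the median just as a patient stopped for toxicity does. A patient with a severe event after 16 doses sits exactly on the monotherapy reference value.

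Section 2.3 says that the safety of this treatment after anti-PD1 therapy needs to be defined. If the report leads with the dose count, a low median could be read as added toxicity when it reflects early progression, and a median near 16 could be read as reassurance whatever the event grades show.

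**Working it through.** **1. Units.** Section 5.2 sets "maximum 14 doses per 5 day cycle". Section 2.2, describing the historical regimen, has it "with a maximum of 14 doses per cycle or 28 doses per course (1 course = 2 cycles", and section 5.1 defines a course in the same way.

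- Course ceiling: 2 × 14 = 28.
- Reference medians as a share of the ceiling: 16/28 = 57% and 15/28 = 54%.
- Rough average per cycle: 16/2 = 8 and 15/2 = 7.5 (halving a course median is only approximate).

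Both medians exceed 14, so they can only be course figures. The per-cycle measure in the opening sentence therefore has no reference value of its own.

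**2. The plan's own figures.** The medians of 16 and 15 come from cited studies and cannot be recomputed from the documents. Section 11.3.5 gives no safety sample size, threshold or power to reproduce.

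**3. Non-toxic routes to a lower course-1 count.**

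| Route | Where the plan allows for it |
|---|---|
| Progression before the end of course 1 | 5.4, 10.1.1 |
| Intercurrent illness, withdrawal, non-compliance | 5.4 |
| Scheduling and local practice | 5.1, footnote to the schedule |
| Institution's own delay and discontinuation criteria | 5.2 |

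All such patients stay in the safety population, and section 11.3.5 does not distinguish their lost doses from doses withheld for toxicity.

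**4. Illustration: shift in the median.** Assumptions, none of them in the documents: course-1 doses in patients who receive both cycles are roughly normal around 16; SD is 2.8 to 4.5 (the stated range spans 26 − 8 = 18, and 18/4 = 4.5); and a fraction f lose cycle 2 for non-toxic reasons and fall below the new median. The median m then solves

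f + (1 − f) × Φ((m − 16)/SD) = 0.5,

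so m is the (0.5 − f)/(1 − f) quantile of N(16, SD).

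| f | Quantile | m, SD 2.8 | m, SD 4.5 |
|---|---|---|---|
| 10% | 0.444 | 15.6 | 15.4 |
| 20% | 0.375 | 15.1 | 14.6 |
| 30% | 0.286 | 14.4 | 13.5 |

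At 20% the drop is 16 − 15.1 = 0.9 to 16 − 14.6 = 1.4 doses. A one-cycle patient has at most 14 doses, so the last assumption holds automatically at 20%. At 30% with SD 4.5 it is slightly strained, because 14 exceeds 13.5.

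**5. Illustration: can the median tell attrition from toxicity?** A simulation with different assumptions (mean 8 doses per cycle, per-cycle SD 2 to 3, correlation 0.5 between cycles, counts rounded and capped at 14) gave a course-1 median of 14 to 15 at 20% loss. With 45 patients and per-cycle SD 2.5, the chance of an observed median of 14 or less was:

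| Scenario | Chance |
|---|---|
| No non-toxic loss, toxicity unchanged | 3% |
| 10% lose cycle 2, toxicity unchanged | 16% |
| 20% lose cycle 2, toxicity unchanged | 45% |
| 30% lose cycle 2, toxicity unchanged | 78% |
| No such loss, but one dose fewer per cycle | 73% |

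Under these assumptions, 30% attrition and a true loss of one dose per cycle look alike.

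**6. Sampling error, for scale.** The approximate 90% margin for a median with n = 45 is 1.645 × 1.2533 × SD/√45. This gives ±0.9 doses at SD 2.8 and ±1.4 at SD 4.5, about the same size as the 20% shift.

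**The case against.** The case for leaving the section alone has real weight.

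- **The comparison may be sound.** A reader might infer that a per-cycle count will be set against 16, a value it could never reach with a ceiling of 14. The documents do not support that reading. The closing sentence names the course-1 median, which is the references' own unit. What stands is the conflict with the opening sentence.
- **CTCAE is not left out.** The same closing sentence places the dose count beside CTCAE toxicity. A reader might also infer that severe or fatal events would go unseen. They would not: adverse events are graded and attributed (6.2), all deaths are reported (6.3.1), boards able to suspend accrual review safety monthly (6.4), and early death from toxicity is a separate outcome category (11.3.3).
- **There is no decision rule.** Section 11.1 calls the drug's safety well studied and makes efficacy the focus. That limits the harm to how safety is described.
- **The attrition figures are assumed.** Cycle 2 falls in week 3 and the scheduled response assessment in week 8, so a progression stop between cycles would be an unscheduled finding in patients with ECOG 0 or 1. The historical minima of 8 and 7 are compatible with one-cycle patients already being in the reference medians, in which case part of the bias is shared. This stands, and it is why the size must be called unknown.
- **Failure to start cycle 2 biases the course count, not doses per cycle actually given.** This is correct. Moving to the course unit therefore helps only if reasons for lost doses are shown as well.
- **Sites are experienced and share published guides (5.2).** This reduces variation in hold practice but does not remove it, since the criteria remain each institution's own and the reference values come from one centre.

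**Conclusion.** The concern holds as an inconsistency in section 11.3.5 and a mismatch with the CTCAE objective in section 1.2. The named primary measure is in a different unit from everything it could be read against. The course-1 count that the section then uses cannot by itself separate toxicity from attrition or local practice.

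The size is not known. If 20% of patients lost cycle 2 for non-toxic reasons, the median would fall by about 0.9 to 1.4 doses. That is about as large as the one-dose gap between the two reference medians and as the sampling margin with 45 patients. It rests on an assumed loss rate, a roughly normal count with SD 2.8 to 4.5, and reference medians free of similar losses.

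The documents do not support two stronger conclusions: that the plan will compare a per-cycle count with 16, or that it will reach a formally wrong safety decision. There is no threshold or test, and CTCAE data are considered alongside. The risk is a misleading description of safety. It is worth correcting before analysis and does not touch the primary efficacy result.

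**What to change.** Amend section 11.3.5 as follows; no treatment rule changes.

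1. Make the primary safety summary the proportion of the safety population whose worst treatment-related CTCAE v4 event is grade 3 or higher, and separately the proportion with a grade 5 event, each with exact 90% limits.
2. Change the unit in the opening sentence from a cycle to course 1, and label that dose count as supportive.
3. Tabulate omitted doses and second cycles not started by reason (toxicity versus other) and by site.
4. Show the course-1 median twice: in all treated patients, and excluding those who lost doses for non-toxic reasons. State that it is unknown whether the reference medians include such patients.

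Cost: a wording change and one reason-for-omission field on the dosing form, if the form does not already have it (the form is not among the documents). Adverse event evaluation is already scheduled. The downside is that the comparison with historical dose counts becomes supportive.

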APPENDIX A – Performance Status Criteria

ECOG Performance Status Scale		Karnofsky Performance Scale	
Grade	Descriptions	Percent	Description
0	Normal activity. Fully active, able to carry on all pre-disease performance without restriction.	100	Normal, no complaints, no evidence of disease.
		90	Able to carry on normal activity; minor signs or symptoms of disease.
1	Symptoms, but ambulatory. Restricted in physically strenuous activity, but ambulatory and able to carry out work of a light or sedentary nature (e.g., light housework, office work).	80	Normal activity with effort; some signs or symptoms of disease.
		70	Cares for self, unable to carry on normal activity or to do active work.
2	In bed <50% of the time. Ambulatory and capable of all self-care, but unable to carry out any work activities. Up and about more than 50% of waking hours.	60	Requires occasional assistance, but is able to care for most of his/her needs.
		50	Requires considerable assistance and frequent medical care.
3	In bed >50% of the time. Capable of only limited self-care, confined to bed or chair more than 50% of waking hours.	40	Disabled, requires special care and assistance.
		30	Severely disabled, hospitalization indicated. Death not imminent.
4	100% bedridden. Completely disabled. Cannot carry on any self-care. Totally confined to bed or chair.	20	Very sick, hospitalization indicated. Death not imminent.
		10	Moribund, fatal processes progressing rapidly.
5	Dead.	0	Dead.
